4.8.3 Pharmacokinetic Parameters

Pharmacokinetic parameters will be calculated by non-compartmental analysis methods from the concentration-time data using Phoenix® WinNonlin® (Version 8.2) or higher following these guidelines:

- Actual time from dose will be used in the calculation of all derived pharmacokinetic parameters, except when parameters are calculated for safety/dose escalation meetings when nominal times may be used to calculate PK parameters.
- There will be no imputation of missing data.
- Any subjects with missing concentration data will be included in the PK analysis set provided that at least C_{max} and AUC_{0-last} can be reliably calculated.
- Pharmacokinetic parameters will be estimated according to the following guidelines:

Table 4-1 Pharmacokinetic Parameter and Estimation

Parameter	Guideline for Derivation
C _{max} , t _{max}	Obtained directly from the observed concentration-time data

Shanghai LianBio Development Co., Ltd. LB2001-101

Statistical Analysis Plan

Parameter	Guideline for Derivation
AUC _{0-last}	The AUC from zero time (pre-dose) to the time of last quantifiable concentration will be calculated by a combination of linear and logarithmic trapezoidal methods. Unless specifically requested and justified the linear up/log down trapezoidal method will be employed.
	The AUC _{0-last} is the sum of areas up to the time of the last quantifiable sample:
	$AUC_{0-last} = \int_0^t C(t)dt$
	The area from zero time extrapolated to infinite time will be calculated as follows:
AUC _{0-inf}	$AUC_{0-inf} = AUC_{0-t} + \frac{C_{t}}{\lambda_{z}}$ where C is the last observed quantifiable concentration
%AUC _{ex}	The percentage of AUC _{0-inf} obtained by extrapolation will be calculated as follows: $%AUC_{ex} = \frac{AUC_{0-inf} - AUC_{0-t}}{AUC_{0-inf}} * 100$
	Unless otherwise determined by PK Scientist's best knowledge and judgment, if the %AUC _{ex} is greater than 30% the value, %AUC _{ex} and all dependent parameters (ie, AUC _{0-inf} , MRT, Vz and CL) will be flagged in listings and excluded from summary tables and statistical analysis of PK parameters, and if the %AUC _{ex} is greater than 20% but less than or equal to 30% the value, %AUC _{ex} and all dependent parameters (ie, AUC _{0-inf} , MRT, Vz and CL) will be flagged in listings, but not excluded from summary tables and statistical analysis of PK parameters. The reason for exclusion will be footnoted in parameter listings.
t ¹ /2	 The apparent terminal phase rate-constant (λz) will be estimated by linear regression of concentration versus time data presented in a log-linear scale. Data are primarily monotonically decreasing in magnitude and are representative of the actual decline in the log concentration-time curve. Only those data points that are judged to describe the terminal log-linear decline will be used in the regression. A minimum number of three data points in the terminal phase will be used in calculating λz with the line of regression starting at any post-C_{max} data point (C_{max} should not be part of the regression slope). Unless otherwise determined by PK Scientist's best knowledge and judgment, if the adjusted correlation coefficient (R² adjusted) is <0.8, it will be excluded from the summary tables and statistical analysis of PK parameters, and λz and all the λz dependent parameters (i.e. t¹/₂, AUC0-inf, CL, MRT, and Vz) will also be flagged and excluded from summary tables and statistical analysis. Any value of R² between 0.8 and 0.9 will be flagged but may be used to determine λz should be equal or greater than 1.5-fold the estimated t¹/₂ or otherwise flagged and used at the PK Scientist's best knowledge and judgement. All derived parameters (i.e. t¹/₂, AUC0-inf, CL, MRT, and Vz) will also be flagged or excluded from statistical analysis of PK parameters accordingly. The reason for flagging and/or exclusion will be footnoted in parameter listings.
	 6. The t¹/₂ will be calculated as follows: t¹/₂ = ln2/λz 7. Data points may be dropped from the linear regression if the PK Scientist considers the reported values to be anomalous. Any data points so designated should remain in the
 	listings with a footnote and be identified in the study report with a rationale for exclusion. Following IV administration systemic clearance of parent drug will be calculated from:
CL or CL/F	$CL = \frac{Dose}{AUC_{0-inf}}$ If desired, apparent clearance (CL/F) following extravascular (eg, oral) dosing

Shanghai LianBio Development Co., Ltd. LB2001-101

Statistical Analysis Plan

Parameter	Guideline for Derivation
	may also be calculated. In the case of steady state administration ${\rm AUC}_{0-\tau}$ will be the denominator.
V _z or V _z /F	Volume of distribution at terminal phase following either intravascular or extravascular dosing may be calculated from:
	$V_z \text{ or } V_z/_F = \frac{Dose}{\lambda_z * AUC_{0-inf}} = CL/_{\lambda_z} \text{ or } (CL/F)/_{\lambda_z}$ Likewise, if derived for steady state
	administration $AUC_{0-\tau}$ will be used.
DNC _{max} , DNAUC ₀₋	DNC_{max} , $DNAUC_{0-last}$ and $DNAUC_{0-inSf}$ divided by dose
_{last} and	
DNAUC _{0-inf}	

PK Parameters Listings:

For final analysis, Biostatistics group will be responsible for reporting individual PK parameters in the listing(s).

Individual PK parameters will be presented to four significant digits, with the exception of t_{max} , which will be presented to two decimal places. Parameters derived directly from source data (e.g. C_{max} ,) shall be reported with the same precision as the source data (if this is not four significant digits).

PK parameters will be listed by-subject for the PKS. PK parameters that will be excluded from summary tables and statistical analyses of PK parameters will be flagged and footnoted with the reason for exclusion.

PK Parameter Summary Tables:

Biostatistics group will use derived PK parameters source data without rounding for calculation of PK parameters summary statistics tables.

PK parameters will be summarized by cohort for the PKS.

Tabular summaries for PK parameters will report N (number of subjects who received treatment) and n (number of subjects with non-missing values).

Descriptive statistics for calculated PK parameters will include N, n, arithmetic mean, SD, CV%, geometric mean, geometric CV%, median, minimum, and maximum values. For t_{max} , only n, median, minimum and maximum values will be presented. No descriptive statistics will be determined when fewer than three individual PK parameters are available.

The rules followed for presentation of PK parameters data with regards to the number of decimal places/significant digits for the listings of subject level PK parameters and summary tables of PK parameters are as follows:

• all summary statistics will be tabulated to a maximum of 4 significant digits, with exception of t_{max} that is presented to 2 decimal places and N and n that will be presented as whole numbers. Comparative estimates will be presented in 3 decimal places and confidence intervals in the form of percentages, CV%, and %AUC_{ex} will be presented to two decimal places.

PK Parameter Figures

To visualize the comparison between each cohort on PK parameter level, Box plots of dosenormalized C_{max} , AUC_{0-last} and AUC_{0-inf} and Dose-Normalized Box plots of C_{max} (PKS), AUC_{0-last} and AUC_{0-inf} will be generated according to CYP2C19 genotype (cohort):

- Figure 4: Box plots of C_{max} (PKS)
- Figure 5: Box plots of AUC_{0-last} (PKS)
- Figure 6: Box plots of AUC_{0-inf} (PKS)
- Figure 7: Dose-Normalized Box plots of C_{max} (PKS)
- Figure 8: Dose-Normalized Box plots of AUC_{0-last} (PKS)
- Figure 9: Dose-Normalized Box plots of AUC_{0-inf} (PKS)

4.8.4 Pharmacokinetic Analysis

To examine the exposure to mavacamten for subjects with the UM/RM/NM vs IM vs PM genotype, analysis of variance (ANOVA) model will be constructed using log-transformed AUC_(0-last), AUC_(0-inf) and C_{max}. The dependent variable will be the ln-transformed primary PK parameters (AUC_(0-last), AUC_(0-inf) and C_{max}) and the independent variables will include fixed effects for cohort and subject as a random effect.

The reference group will be cohort 1 and test groups will be cohort 2 to cohort 4. Geometric leastsquares means for each cohort (cohort 1 and cohort2:UM/RM/NM, cohort 3:IM, cohort 4: PM), point estimates and associated 90% CIs for the ratios for each primary PK parameter will be produced in tabular format. Estimates of between -participant variability (%CVb) will also be provided.

4.8.5 **Population PK (PopPK) Analysis**

PopPK analysis will be conducted with the pooled data from the current study LB2001-101 and other mavacamten studies. Additional details on PopPK model development and analysis will be provided in a separate PopPK data analysis plan(DAP).

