6.4 Administration

All subjects will receive mavacamten in an open-label manner.

The IMP for this clinical study is mavacamten. Study medication throughout this protocol refers to IMP as well as any other protocol-required medications (note that for this protocol, there are no other required study medications).

Mavacamten will be administered at the CRU by a trained, qualified staff member. Subjects will receive a single dose of mavacamten on Day 1.

Subjects should take mavacamten with approximately 240 mL of water. Subjects should fast overnight (for at least 8 hours) before taking mavacamten and should not eat any food until 3 hours after taking mavacamten. Water will be allowed except for 1 hour before and after dosing.

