10.3.6 Pharmacokinetic Analysis

All PK analyses will be conducted in the pharmacokinetics set. The plasma concentration-time data of mavacamten for individual subject will be listed and displayed graphically in the linear and semi-log scales. The plasma concentration-time data for each cohort will be summarized descriptively in tabular and the mean concentration-time curve will be plotted on the linear and semi-log scales by cohort. The PK parameter data will be listed and summarized descriptively in tabular format by cohort. Statistics include the number of subjects, arithmetic mean, GM, SD, and CV, min, median, and max.

Effect of different CYP2C19 genotypes (UM/RM/NM vs IM vs PM)

To examine the exposure to mavacamten for subjects with the UM/RM/NM vs IM vs PM genotype, analysis of variance (ANOVA) model will be constructed using log-transformed AUC_(0-last), AUC_(0-inf) and C_{max}. The AUC_(0-last), AUC_(0-inf) and C_{max} will be compared between the cohort 1 and cohort 2 (CYP2C19 UM/RM/NM), cohort 3 (CYP2C19 IM), and cohort 4 (CYP2C19 PM). The reference group will be cohort 1 and test groups will be cohort 2 to cohort

4 and the GM ratios of each parameter between all cohorts and the corresponding 2-sided 90% confidence intervals will be calculated.

Further details are presented in the SAP.

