3 INVESTIGATIONAL PLAN

3.1 Overall Study Design

This is an open-label, parallel-group, single-center Phase 1 clinical trial. Healthy adult Chinese subjects with different CYP2C19 genotypes (Cohort 1 and Cohort 2: CYP2C19 ultra-rapid metabolizer (UM), rapid metabolizer (RM), or normal metabolizer (NM); Cohort 3: CYP2C19 intermediate metabolizer (IM); Cohort 4: CYP2C19 poor metabolizer (PM)) will be included and administered with a single oral dose of mavacamten to evaluate its PK profile. The doses administered include: 15 mg for cohort 1; 25 mg for Cohort 2; 15 mg for Cohort 3; 15 mg for Cohort 4. Blood samples will be collected from subjects at scheduled time points for PK testing. Series of safety assessments (including but not limited to AEs, laboratory tests, vital signs, and ECGs) will be performed during the whole study at specified time points.

Shanghai LianBio Development Co., Ltd. LB2001-101

```
Statistical Analysis Plan
```

Abbreviations: CYP = Cytochrome P450; EOS = end of study; IM = intermediate metabolizer; NM = normal metabolizer; PM = poor metabolizer; RM = rapid metabolizer; UM = ultra-rapid metabolizer.

Approximately 44 healthy adult Chinese subjects with different CYP2C19 genotypes will be enrolled in this clinical trial. This is a single-center study. Subjects will be divided into 4 cohorts.

- Cohorts 1 and 2: 12 healthy adult Chinese subjects to ensure that data will be obtained for at least 10 subjects; with their CYP2C19 genotypes being:
 - CYP2C19 UM: *17/*17 or
 - CYP2C19 RM: *1/*17 or
 - CYP2C19 NM: *1/*1;
- Cohort 3: 12 healthy adult Chinese subjects to ensure that data will be obtained for at least 10 subjects; with their CYP2C19 genotypes being:
 - CYP2C19 IM: *1/*2 or *1/*3;
- Cohort 4: 8 healthy adult Chinese subjects to ensure that data will be obtained for at least 6 subjects; with their CYP2C19 genotypes being:
 - CYP2C19 PM: *2/*2, *3/*3, or *2/*3.

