4.12 Determination of Sample Size

No formal hypothesis testing will be conducted. The number of subjects in each cohort is expected to provide sufficient data to allow the assessment of the safety, tolerability and PK profile of mavacamten in Chinese subjects. Hence approximately 8-12 subjects will be enrolled in Phase I to obtain adequate PK and safety data based on China regulatory consideration.

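### SAP 4.8.4 fits a random subject effect to one value per subject and does not say which variance %CVb uses; if it is the subject component, the data cannot determine it

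*SAP*

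**What the plan says.** SAP 4.8.4 models the log-transformed AUC(0-last), AUC(0-inf) and Cmax. On the right-hand side, "the independent variables will include fixed effects for cohort and subject as a random effect". Cohort 1 is the reference, and ratios for Cohorts 2 to 4 are given with 90% CIs. The section ends: "Estimates of between -participant variability (%CVb) will also be provided". It names no variance component, formula or degrees-of-freedom method.

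Protocol 10.3.6 says only that an "analysis of variance (ANOVA) model will be constructed using log-transformed" values of the same three parameters and that the cohorts will be compared. It mentions no subject term and adds: "Further details are presented in the SAP".

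On the design, SAP 3.1 states: "This is an open-label, parallel-group, single-center Phase 1 clinical trial". Protocol 6.4 states: "Subjects will receive a single dose of mavacamten on Day 1".

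Two other SAP sections bear on variability. Section 4.8.1 gives a geometric CV formula, sqrt(exp(s²) − 1) × 100 with s the SD of the logged values, for the concentration summaries. Section 4.8.3 plans by-cohort summaries of the PK parameters: "Descriptive statistics for calculated PK parameters will include N, n, arithmetic mean, SD, CV%, geometric mean, geometric CV"%. Neither is linked to %CVb.

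**The concern.** A random subject effect separates between-subject from within-subject variance when subjects are measured more than once, as in a crossover. Here each subject has one dose, one profile and one value per parameter, so the model has as many random subject levels as observations and the split between subject and residual is arbitrary.

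Because the SAP names a subject effect and then promises a between-participant CV from the same model, reading %CVb from the subject component is natural. That is the reading the data cannot support. Two programmers could follow the text and report different %CVb values from the same data. The redundant term also leaves the error degrees of freedom open and can upset software that tries to estimate both components.

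**Working it through.** **Plan's own figure.** The documents give no %CVb value and no power calculation. The one number to reproduce is the sample size: 12 + 12 + 12 + 8 = 44 (protocol 10.1), which agrees. The planned minimum is 10 + 10 + 10 + 6 = 36.

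**Structure.** With one value per subject, the subject design matrix is the identity. The covariance matrix is V = (σ²_subject + σ²_residual) × I, so the likelihood depends only on the sum. The information matrix for the two components has rank 1.

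**Inputs (assumption).** The geometric CVs in protocol Table 3, from 8-subject cohorts of earlier studies, stand in for this trial. UM/RM/NM values are used for Cohorts 1 and 2, IM 15 mg for Cohort 3 and PM 15 mg for Cohort 4.

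| Parameter | UM/RM/NM Japanese | UM/RM/NM Caucasian | IM | PM |
|---|---|---|---|---|
| Cmax | 18.3% | 28.6% | 19.8% | 31.4% |
| AUC(0-last) | 30.8% | 49.6% | 25.4% | 13.6% |
| AUC(0-inf) | 34.0% | 53.2% | 27.4% | 20.3% |

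**Pooled log-variance.** Each log-variance is ln(1 + gCV²), weighted by n − 1. For AUC(0-last) with Japanese values:

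- Cohorts 1 and 2: ln(1 + 0.308²) = 0.0906; Cohort 3: 0.0625; Cohort 4: 0.0183.
- N = 44: (11 × 0.0906 + 11 × 0.0906 + 11 × 0.0625 + 7 × 0.0183)/40 = 0.0702.
- N = 36, with weights 9, 9, 9, 5 over 32: 0.0714.

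**%CVb from the total variance**, 100 × sqrt(exp(pooled variance) − 1), N = 44:

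| UM/RM/NM values used | Cmax | AUC(0-last) | AUC(0-inf) |
|---|---|---|---|
| Japanese | 21.5% | 27.0% | 30.2% |
| Caucasian | 27.0% | 39.0% | 42.2% |

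**%CVb from the subject component**, 100 × sqrt(exp(f × 0.0702) − 1), where f is the share of variance given to subject (AUC(0-last), Japanese values, N = 44):

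| f | %CVb | REML log-likelihood | SE of ln ratio, Cohort 4/1 |
|---|---|---|---|
| 0 | 0% | −8.41 | 0.121 |
| 0.25 | 13.3% | −8.41 | 0.121 |
| 0.50 | 18.9% | −8.41 | 0.121 |
| 0.75 | 23.3% | −8.41 | 0.121 |
| 1 | 27.0% | −8.41 | 0.121 |

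The SE is sqrt(0.0702 × (1/12 + 1/8)) = 0.121. For Cohorts 2/1 and 3/1 it is sqrt(0.0702 × (1/12 + 1/12)) = 0.108. Neither changes with f. With N = 36 the %CVb range is 0 to 27.2% and the Cohort 4/1 SE is sqrt(0.0714 × (1/10 + 1/6)) = 0.138.

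**What software may do.** A mixed model was fitted to 44 constructed ln AUC(0-inf) values with the Table 3 CVs (total variance 0.0871). It warned of a non-positive-definite Hessian and split the variance equally, 0.0436 each. Read from the subject part, %CVb is 21.1%; from the total it is 30.2%. The same fit printed SEs of 0.109, 0.088 and 0.106 for the three log ratios, where the model-based values are 0.1205, 0.1205 and 0.1347. That is a numerical artefact of the singular fit, not a property of the model.

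**Degrees of freedom.** Cohort alone gives 44 − 4 = 40, or 36 − 4 = 32. A rule of N minus the rank of fixed plus random columns gives 44 − 44 = 0. If normal limits were used instead of t, the 90% CI factors, exp(±quantile × SE), for Cohort 4/1 AUC(0-last) would change little:

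- N = 44: 0.820–1.220 (normal) against 0.816–1.226 (t, 40 df).
- N = 36: 0.797–1.255 (normal) against 0.792–1.263 (t, 32 df).

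**The case against.** The strongest reply is that only the total variance can be estimated, so a competent analyst would report %CVb from it. SAP 4.8.1 already shows the log-scale conversion, and taking subject as the error term itself gives the same single number. On this view only a label is undefined. It is true that the total-variance reading is well defined. But the 4.8.1 formula is given for concentration summaries and does not settle which variance %CVb uses, and a literal fit can return another value, as the equal split shows.

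A second reply is that protocol 10.3.6 lists no model terms, so it cannot be cited as specifying a cohort-only model. That is fair: a cohort-only ANOVA is consistent with the protocol, which leaves the details to the SAP.

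Third, the 0-to-27% range describes a flat likelihood under borrowed CVs and does not forecast what would be reported. The degrees-of-freedom problem is also hypothetical, because the SAP names no rule. Both points stand and limit the weight of the finding.

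Last, the consequence is small. SAP 4.12 says "No formal hypothesis testing will be conducted", and the by-cohort geometric CV% is more informative than a pooled figure. This also stands. One sentence defining %CVb from the total variance would remove the main ambiguity, but the redundant term would remain in the model.

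**Conclusion.** The concern holds and is minor. As written, the model is over-parameterised, and the %CVb for the three primary PK parameters is not determined if it is taken from the subject component. That conclusion follows from the design and needs no numerical assumption. The sizes do: under the Table 3 CVs with 44 evaluable subjects, the undetermined range for AUC(0-last) runs from 0 to 27.0% with the Japanese UM/RM/NM values, or to 39.0% with the Caucasian values.

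The geometric mean ratios and their model standard errors are unaffected. The 90% CIs would be affected only under some degrees-of-freedom rules, or if standard errors from a singular fit were used unchecked. Variability by genotype still reaches the report through the by-cohort geometric CV%.

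**What to change.** In SAP 4.8.4:

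1. Remove the random subject term and fit ln(parameter) with cohort as the only effect. The error df are then 40 with 44 evaluable subjects and 32 with 36.
2. State %CVb = 100 × sqrt(exp(residual mean square) − 1).
3. Note that with one dose per subject this is pooled total variability: between-subject, within-subject and assay variation together.

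The cost is SAP wording only, with no change to data, sample size, ratio estimates or their model standard errors. The pooled figure averages over cohorts whose variability may differ and does not isolate between-participant variation, so the by-cohort geometric CV% in SAP 4.8.3 should stay as planned.

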4.9 Safety Evaluation

All safety summaries and analyses will be based upon the SAS as defined in Section 4.4.1.

4.9.1 Adverse Events

Adverse events will be coded using the Medical Dictionary for Regulatory Activities (MedDRA) Version 23.1 or higher.

All AE summaries should provide the number and percentages of subjects reporting at least one AE and the total number of events reported.

Summaries of AEs will include the following:

- Incidence of AEs Overview (by cohort and overall)
- Incidence of drug taken period AEs(by cohort and overall, SOC, and PT)
- Incidence of drug taken period AEs by maximum relationship (by cohort and overall, SOC, and PT)
- Incidence of drug taken period AEs by maximum severity (mild/moderate/severe, by cohort and overall, SOC, and PT)

• Incidence of AESIs (by cohort and overall, SOC, and PT)

Summary tables will contain counts of subjects, percentages of subjects in parentheses, and the number of events where applicable. A subject who has multiple events in the same SOC and PT will be counted only once in the subject counts, but all events will be included.

A by-subject listing of all adverse events (including non-treatment-emergent events) will be provided. This listing will be presented by cohort and will include: subject identifier, age, sex, race, adverse event (SOC, PT, and verbatim term), date of onset, date of resolution, duration, severity, seriousness, action taken, outcome and causality.

All Adverse Events (AEs)

All AEs will be listed including pre-treatment AEs, and pre-treatment SAE will be listed separately.

Drug Taken Period Adverse Event

Drug taken period AEs will be summarized by SOC and PT, including the number and percentage of subjects experiencing events, separately.

Severity

Drug taken period AEs will be summarized by SOC, PT, and severity, including the number and percentage of subjects experiencing events. If a subject reports the same drug taken period AE more than once within that SOC and PT, the drug taken period AE with the highest severity will be used in the corresponding severity summaries.

In summaries including severity, the following intensity categories will be summarized: 'Mild', 'Moderate', 'Severe'. Subjects who experience the same event multiple times will be included in the most severe category. Events with missing intensity will be considered as 'Severe' events for summary purposes but recorded as missing in the listings.

Relationship (Causality)

Drug taken period AEs will be summarized by SOC, PT, and causality, including the number and percentage of subjects experiencing events. Relationship to study drug will be tabulated respectively. In summaries including severity, the following relationships will be summarized: 'unrelated', 'Related'. If a subject reports the same drug taken period AE more than once within that SOC and PT, the drug taken period AE with the worst case relationship to study drug will be used in the corresponding relationship summaries. Events with missing relationship will be considered as 'Related' to the last given study drug for summary purposes but recorded as missing in the listings.

Adverse Events of Special Interests (AESIs)

Adverse events of special interests (AESIs) will be summarized by SOC and PT, including the number and percentage of subjects experiencing events. Listing of AESI will be provided.

